development of a robust, clinically feasible rsfMRI data analysis pipeline, this study is expected to result in improved understanding of the functional reorganization that takes place during and after intervention.

4. Study Procedures

- Study design, including the sequence and timing of study procedures (distinguish research procedures from those that are part of routine care).

This will be an early phase 1 (phase 0) clinical trial. Specifically, the study will be performed as a randomized, parallel group trial to determine if the amount of changes in brain functional connectivity outcome measures (i.e., between network connectivity) is significantly different between the group of patients that perform FES cycling and another group of patients that perform passive (sham) cycling.

Patients of the International Center for Spinal Cord Injury (ICSCI) at the Kennedy Krieger Institute (KKI) will be identified as meeting the inclusion criteria by reviewing the medical records held by the ICSCI. Once the patient consents by signing the consent form, official screening of subjects will be performed. Subjects will be randomized into 2 groups: FES cycling (Group 1; n=24) and passive cycling (Group 2; n=24). The patients will undergo either an FES cycling or a passive cycling sessions for 4 weeks, 3 times a week. **Acquisition of rsfMRI measures:** MRI will be performed on all participants at the beginning (prior to cycling sessions) and at the end of the 2nd and 4th weeks of the intervention program. **Acquisition of clinical measures:** ISNCSCI and SCIM (Spinal Cord Independence Measure) evaluations will be performed to coincide with the dates of MRI acquisitions, to determine the neurological level and the degree of sensory and motor impairments. Detailed study timeline can be found in Figure 1.

[figure not shown]

Figure 1. Study Timeline.

- SCI patients assigned to FES cycling group will take part in the following evaluations:
 - Medical chart review / MRI screening questionnaire
 - FES cycling trial
 - Neurological evaluation (ISNCSCI – more commonly known as ASIA exam)
 - Functional evaluation (SCIM)
 - MRI

Date: 4.14.2023

Principal Investigator: [name].

Application Number: IRB000182576

E1: FES cycling

- SCI patients assigned to passive cycling group will take part in the following evaluations:
 - A: Medical chart review / MRI screening questionnaire
 - B2: Passive cycling trial

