 - C1: Neurological evaluation (ISNCSCI – more commonly known as ASIA exam)
 - C2: Functional evaluation (SCIM)
 - D: MRI
 - E2: passive cycling

A: Medical chart review / MRI screening questionnaire

For all subjects with spinal cord injury, their medical chart will be reviewed for the following information:

Demographics

Medical history (including labs)

Physical history

Neurological history

Medication history

Therapeutic plan

Physical/occupational/aquatic therapy history (including outcome measures)

This information is obtained as part of a routine care. The participant does not have to be physically present during this process. At this time, a standard MRI screening questionnaire will also be completed to be sure that it is safe for the participant to have an MRI exam.

B: Cycling trial

B1. FES cycling trial: This is a routine exam performed for people with spinal cord injury at the ICSCI.

Once medically cleared to start an exercise program, subjects who are assigned to the FES cycling group will undergo a trial use of the FES cycle. This trial of FES will be overseen by a trained physical therapist experienced at setting up the FES cycle. The goal of this will be to ensure that the patient is willing and able to use the cycle. Participants who fail the FES trial will be excluded from the study. For additional details regarding the FES component, please see the **E: Cycling** section below. If the patient has successfully participated in an FES cycling program previously, this step will be omitted.

B2. Passive cycling trial: This is a routine exam performed for people with spinal cord injury at the ICSCI.

Once medically cleared to start an exercise program, subjects who are assigned to the passive cycling group will undergo a trial use of the FES cycle (**but with the stimulation component OFF**). This trial of passive cycling will be overseen by a trained physical therapist experienced at setting up the FES cycle. The goal of this will be to ensure that the patient is willing and able to use the cycle. Participants who fail the passive cycling trial will be excluded from the study. For additional details, please see the **E: Cycling** section below. If the patient has successfully participated in an FES cycling program previously (with or without the stimulation component), this step will be omitted.

C: Neurological evaluation

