E1. Functional Electrical Stimulation cycling: The FES cycling group (Group 1) will use RT300 ergometer (Restorative Therapies, Inc., Baltimore, Maryland). The RT300 ergometers are currently installed at ICSCI according to Kennedy Krieger Institute and Johns Hopkins Hospital safety guidelines. The muscles chosen for stimulation will be the bilateral glutei, quadriceps and hamstrings. The FES stimulation parameters will be set as follows: waveform biphasic, charged balanced; phase duration typically of 250 microseconds; pulse rate 33 to 45 pulses per sec (pps). The stimulus intensity of each channel will be adjusted for individual patients and muscle group so that a tolerable stimulation is provided that will generate a cycling action (0-140 mA). Target cycling speed is 50 RPM. Resistance will be automatically adjusted by the FES bike according to the subject's performance. When fatigue occurs, participants will continue cycling with electrical stimulation and motor support. FES therapy will be administered for one hour per session 3 times a week.

E2. Passive cycling: The passive cycling group (Group 2) will use the same RTI 300 ergometer however during this period stimulation will not be turned on. Instead, continuous motor support will be activated resulting in passive cycling. Target cycling speed is 50 RPM. Participants assigned to passive cycling will be required to have one hour of passive therapy 3 times a week for the entire duration of treatment assignment.

b. Study duration and number of study visits required of research participants.

Patients will be evaluated for appropriateness of enrollment and informed consent will be obtained. During the next 8 weeks, the screening process will be completed. A trial of FES will be performed at Kennedy Krieger Institute ICSCI to ensure that the participant is able to tolerate the stimulations of this exercise modality. If he or she is willing and able to proceed with the study then baseline data will be obtained at the beginning of week 1. The detailed study timeline can be found in Figure 1. The study duration for each assessment is as follows:

A: Medical chart review: N/A

B: FES/passive cycling trial (30 min)

C1: Neurological evaluation (up to 1 hour, part of routine care in ICSCI; total of 3 times over 4 weeks)

C2: Functional evaluation (up to 45 min, part of routine care in ICSCI; total of 3 times over 4 weeks; to be performed simultaneously during one of E1 or E2 sessions)

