D: MRI (up to 90 minutes; total of 3 times over 4 weeks)

E1: FES cycling (1 hour, 3 times a week)

E2: Passive cycling (1 hour, 3 times a week)

We expect to enroll an average of 4 subjects each month into the trial with a total number of subjects of 48 (24 per group). Since participants will be enrolled in the study for 4 weeks, then the entire duration of the study will be around 1.5 years. After completing 24 subjects enrollment will be paused for interim analysis when it will be decided whether enrollment will continue.

c. Blinding, including justification for blinding or not blinding the trial, if applicable.

Because of the nature of the interventions (i.e., electrical stimulation), study participants cannot be completely blinded to the treatment they will receive. This is because many participants will have a residual motor and sensory functions and 'feel' which intervention they are receiving. Therefore, this study will be

Date: 4.14.2023

Principal Investigator: [name].

Application Number: IRB000182576

performed as a single-blinded randomized trial. Study physicians and research staff who perform study measurements on participants will be blinded from the intervention the study participants receive.

- d. Justification of why participants will not receive routine care or will have current therapy stopped.

All participants will receive routine care for treatment of spinal cord injury. Participants will not be asked to stop their current medications or therapy. All subjects will continue to consistently perform their usual (“baseline”) amount of physical activity throughout the study, including home exercise stretching program, cardiovascular conditioning, etc. “Baseline” activity is defined as amount of physical activity performed for at least 1 month prior to enrollment. Routine care will not be interrupted.

- e. Justification for inclusion of a placebo or non-treatment group.

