Application Number: JRB000182576

included only if one can understand the nature of the experiment as presented in English, and can cooperate with symptom assessment in English. 48 subjects will be recruited in total over a period of two years.

Inclusion criteria:

- Adult (18-99 years) men and women of all ethnic groups
- SCI, traumatic
- Thoracic (T1-T12) and lumbar (L1, L2), without the involvement of lower motor neurons.
- ASIA classification A-D
- Chronic injury: > 6 months from the injury
- Satisfactory general health
- No FES ergometer (i.e. RT300 or equivalent) use within 4 weeks.
- Ability to comply with procedures and follow-up

Exclusion criteria:

- Contra-indication to MR study (*e.g.*, cardiac pacemaker, claustrophobia, aneurysm clip, etc.)
- History or clinical evidence of moderate or severe brain injury
- Major spine deformity (*e.g.* scoliosis, kyphosis, subluxation)
- Movement disorder or severe spasticity preventing ability to lay still for extended periods required for imaging.
- Women who are pregnant
- Concurrent lower motor neuron disease such as peripheral neuropathy that would exclude lower extremity electrical excitability
- Unstable long bone fractures of the lower extremities.
- Subjects with history of inability to tolerate electrical stimulation.

Pregnancy is associated with significant physiological deviations with respect to cerebral spinal fluid dynamics and blood flow in the middle cerebral artery that are different than what is seen in women who are not pregnant. Gonadal steroids associated with pregnancy are also implicated in marked changes in cognitive function. Because of the significant changes from the normal, non-pregnant condition it is important to exclude pregnant women from many studies. If they were not excluded their data would significantly add to the variance of the physiological and behavioral measures. Furthermore, that variance is not readily interpreted at this time.

6. Drugs/ Substances/ Devices

- a. The rationale for choosing the drug and dose or for choosing the device to be used.

The RT-300 FES bike has been FDA-cleared for use in general rehabilitation (the device clearance number is K072398). It has been a standard rehabilitation treatment modality at our center for several years.

- b. Justification and safety information if FDA approved drugs will be administered for non-FDA approved indications or if doses or routes of administration or participant populations are changed.

N/A

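### As written, baseline MRI and ISNCSCI follow assignment and an arm-specific cycling trial; they should be completed before both

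*Combined protocol and SAP*

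**What the plan says.** The order of events has to be pieced together from several places.

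- **Section 4a, study design.** After consent and screening, patients are randomised, 24 to each arm. The first MRI falls before the cycling sessions, and ISNCSCI and SCIM are tied to the MRI dates.
- **Section 4a, B1.** "subjects who are assigned to the FES cycling group will undergo a trial use of the FES cycle". The step is skipped for a patient with earlier successful FES cycling.
- **Section 4a, B2.** "subjects who are assigned to the passive cycling group will undergo a trial use of the FES cycle", "but with the stimulation component OFF".
- **Section 4b.** Screening may take 8 weeks after consent. A trial of tolerance to stimulation is described without naming an arm. For a patient who can and will go on, "then baseline data will be obtained at the beginning of week 1". The list of durations then gives 30 minutes for the FES or passive trial, and places SCIM so as "to be performed simultaneously during one of E1 or E2 sessions".
- **Section 4c.** "study participants cannot be completely blinded to the treatment they will receive", because many of them will feel which treatment it is. Staff who take the measurements are to be blinded.
- **Section 5.** One inclusion criterion reads "No FES ergometer (i.e. RT300 or equivalent) use within 4 weeks", with no date from which the 4 weeks are counted.

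Sections 4a and 4b refer to Figure 1 for the detailed timeline. It is not shown in the text available here.

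**The concern.** A baseline is useful in a randomised comparison because the allocation cannot have influenced it. Here it seems that the allocation can, by two routes. A patient who has been through the arm-specific trial may have felt which arm it is, and the ISNCSCI then asks for muscle effort and for reports of touch and pinprick. And an FES-arm patient who took the trial has had stimulation before the first scan, in a study whose premise is that connectivity responds early.

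What is at stake is the change from baseline. Section 4a frames the trial as a comparison of the amount of change in connectivity between arms. Aim 2 correlates the week-2 change in BNC with the week-4 change in ISNCSCI, and both changes start from this visit.

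**Working it through.** **1. Sequence.** Put side by side, B1 and B2 in 4a give the trial to patients already assigned, and 4b places baseline after a trial. The order is assignment, arm-specific trial, baseline. The rule in 4a that the first MRI precedes the cycling sessions does not alter this, because the trial (item B) is listed separately from the sessions (items E1 and E2). No visible text places baseline before item B.

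**2. How a shift enters the result.** Let Δ be the between-arm difference in change measured from an untouched baseline, and let s_F and s_P be the mean shifts in baseline in the FES and passive arms caused by the trial or by awareness. With the follow-up values held fixed, the observed difference in change is

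Δ − (s_F − s_P).

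A shift common to both arms cancels; one that differs between arms passes through one-for-one with opposite sign. If only a fraction p of the FES arm takes the stimulated trial, and each such patient shifts by s, that route contributes s_F = p·s. The documents give neither p nor s.

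**3. Size of the exposure.** Inputs from section 4: trial 30 minutes; sessions of 1 hour, 3 times a week, for 4 weeks.

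- Scheduled by week 2: 2 × 3 × 1 h = 6 h, and 0.5/6 = 8.3%.
- Scheduled by week 4: 4 × 3 × 1 h = 12 h, and 0.5/12 = 4.2%.

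These are upper bounds on exposure time, since 30 minutes is the length of the trial and not of the stimulation. They are not estimates of bias. The interval from trial to baseline is not stated.

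**4. Illustration under an assumption.** The plan gives no figure for this point. Its sample size (24 subjects, 80% power, alpha 0.018 in section 7c) is roughly what a correlation test gives if the effect is the pilot R² of 0.35. With r = √0.35 = 0.592 and n = ((z_α + z_β)/atanh r)² + 3, the result is 25.2 two-sided and 21.7 one-sided. Power for the between-arm contrast is therefore not stated. Suppose that contrast had exactly 80% power with 24 per arm at two-sided alpha 0.018. The standardised difference would be (2.366 + 0.842) × √(2/24) = 0.93. If pre-baseline exposure concealed part of it, power would be:

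| Part concealed | Power |
|---|---|
| 0% | 80% |
| 5% | 75% |
| 10% | 70% |
| 20% | 58% |

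Nothing in the documents says which row applies, and the first may.

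**5. Places that do not agree.**

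- *Who is stimulated in the trial.* B1 and B2 make it arm-specific. The narrative in 4b names no arm and sits within screening, yet the list in 4b again names an FES and a passive trial.
- *SCIM.* The study design text in 4a puts it on the MRI dates, the first of which precedes cycling. Item C2 in 4a and the list in 4b put it inside cycling sessions. Section 7b lists a baseline SCIM.
- *FES-free period.* Section 5 gives no reference date.

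**The case against.** The strongest reply is that the text supports less than it first suggests, and much of that reply stands.

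- A reader might infer that every patient knows the arm at baseline. No section says when patients are told. Section 4c says that many will feel the treatment, not all, and patients with little sensation or whose trial is omitted may not know. The awareness route also bears on ISNCSCI more than on BNC. Assessor blinding helps with scoring, but it does not remove the patient's own awareness.
- A reader might infer that the whole FES arm, and only that arm, is stimulated before baseline. Patients with earlier FES cycling skip the trial, and the at-home option in 4a shows that such patients are expected. On the wider reading of 4b, patients in either arm could be stimulated. An arm-specific shift from stimulation would then largely disappear, but the baseline of those trialled would still not be free of stimulation.
- A reader might infer that the trial breaches the inclusion criterion. It does so only if the 4 weeks are counted back from baseline, and section 5 does not say so.
- A reader might infer a loss of randomised patients who prove unfit for MRI. The MRI questionnaire, the exclusions in section 5 and screening before randomisation largely deal with this.
- A reader might infer a false positive. No carry-over from one session is documented. If there were one in the direction of the treatment effect, it would shrink the FES change.
- Section 7c plans no baseline adjustment and no between-arm test of ISNCSCI. The reliance on change comes from 4a and Aim 2. SCIM is a secondary outcome, so that conflict is one of wording.

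Figure 1 might settle the order. If so, the text should be brought into line with it.

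**Conclusion.** The point holds in limited form. On the visible text, baseline MRI and ISNCSCI are post-randomisation. They may be taken from patients many of whom have already felt their arm, and for some FES-arm patients they follow a stimulated session. A possible arm-specific shift therefore sits inside each change score used for the between-group question and for Aim 2.

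Neither its size nor its direction can be derived from the documents, and it may be negligible. The only firm figure is the ceiling on exposure, 0.5 h against 6 h by week 2. The conclusion rests on B1 and B2 meaning what they say about assigned patients, and on Figure 1 not showing a different order. The case for acting is that the weakness is avoidable at little cost, not that bias has been shown.

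**What to change.** In sections 4a and 4b, state that baseline MRI and ISNCSCI are completed before the assignment is disclosed and before the arm-specific cycling trial. State the intervals between baseline, trial and first session.

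In the same revision:

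- reconcile 4a and 4b on whether the trial is arm-specific and who is stimulated in it;
- give the reference date for the 4-week no-FES criterion in section 5;
- reconcile the study design text in 4a with item C2 and the list in 4b on when the first SCIM is done.

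For patients already enrolled, record whether the trial was done, whether it was stimulated, and when it took place relative to baseline, so that the exposure can be described and examined.

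The cost is wording and visit order. No assessment is added, but a few baseline scans will be spent on patients who then fail the trial. The change does not remove patients' awareness at weeks 2 and 4, which section 4c accepts; it protects only the starting point.

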C1. American Spinal Injury Association (ASIA) Impairment Scale (ISNCSCI) evaluation: American Spinal Injury Association (ASIA) Impairment Scale (ISNCSCI) evaluation is part of a routine care

Date: 4.14.2023

Principal Investigator: [name].

Application Number: IRB000182576

evaluation performed for SCI patients at the International Center for Spinal Cord Injury (ICSCI) at Kennedy Krieger Institute. While its formal name is ISNCSCI, it is more commonly referred to as the ASIA exam. The evaluation consists of: 1) a motor component, where strength of ten key muscles (elbow flexors, wrist extensors, elbow extensors, finger flexors, finger abductors, hip flexors, knee extensors, ankle dorsiflexors, long toe extensors, and ankle plantar flexors) on each side of the body is evaluated, and 2) a sensory component, where touch and pinprick sensations are tested on 28 dermatomes on each side of the body. The total evaluation time will not exceed 60 minutes.

C2. Spinal Cord Independence Measure Version III (SCIM-III): The Spinal Cord Independence Measure Version III (SCIM-III) is a part of a routine care evaluation performed for individuals with SCI that assesses daily living and mobility activity performances. Specifically, it assesses the degree of self-care (feeding, grooming, bathing, and dressing), respiration and sphincter management, and mobility abilities (bed and transfers and indoors/outdoors). SCIM-III is frequently used in both clinical practice and clinical trial settings and is used to help guide clinicians in determining treatment goals and objectives for patients with an SCI. The SCIM takes approximately 30-45 mins to administer and score. However, the assessment will concurrently during the study participants' FES biking session, and will not contribute any additional time to the total study duration.

D: Magnetic Resonance Imaging (MRI)

This is a research procedure and not part of a routine care. All MR imaging will be performed at the F.M. Kirby Research Center using 3T scanners and consist of two main components: structural imaging of brain and spine, and functional imaging of brain and spine. Prior to imaging, an MRI technician will always perform an in-person safety screening, during which time any contraindications to MRI (e.g., aneurysm clips, pacemaker, etc.) will be identified. The total MR scan time will not exceed 90 minutes.

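### SCIM is scheduled inside the participant's own cycling session with no masking described, so the assessor blinding stated in Section 4c has no basis for this secondary outcome

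*Combined protocol and SAP*

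**What the plan says.** Section 4c calls the trial single-blinded. It accepts that participants cannot be completely blinded and places the blinding with the staff: "Study physicians and research staff who perform study measurements on participants will be blinded from the intervention the study participants receive". It makes no exception for SCIM.

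Section 7b lists SCIM as a secondary outcome at baseline, mid-intervention and post-intervention. Section 4b gives its timing as "to be performed simultaneously during one of E1 or E2 sessions". The C2 description in Section 4a agrees: the assessment runs during the participant's "FES biking session, and will not contribute any additional time to the total study duration".

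E1 is cycling with electrical stimulation of the glutei, quadriceps and hamstrings. E2 uses the same ergometer, "however during this period stimulation will not be turned on", and the motor drives the movement.

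On dates, the study design text in Section 4a says that "MRI will be performed on all participants at the beginning (prior to cycling sessions") and again at the end of weeks 2 and 4. It adds that the ISNCSCI and SCIM "evaluations will be performed to coincide with the dates of MRI acquisitions".

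**The concern.** The two arms differ in whether stimulation is on during the cycling session. That session is where an observer is most likely to learn the allocation, and it is where the schedule puts SCIM. A rater who is there while the participant cycles may see stimulation being delivered or adjusted, or see that there is none.

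Because participants are not fully blinded, the single-blind label rests on the measurement staff. A reader of Section 4c would take a between-arm SCIM comparison as assessor-blinded, and the schedule gives no ground for that.

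The in-session rule also affects the baseline. A SCIM taken during an E1 or E2 session comes, at the earliest, during the participant's first exposure to the assigned intervention.

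**Working it through.** The documents give no figure to reproduce here, so the check sets the passages side by side.

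1. **Does the blinding statement cover SCIM?** Section 4c covers physicians and research staff who perform study measurements. SCIM is a listed outcome (Section 7b). Section 4a labels it routine care, but it gives ISNCSCI, a primary outcome, the same label. The label therefore cannot by itself take a measure outside Section 4c.

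2. **When is SCIM done?** Section 4b names E1 and E2, so the in-session rule applies to both arms. C2 confirms that it overlaps with cycling.

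3. **Is the overlap practicable as written?** "The SCIM takes approximately 30-45 mins to administer and score", and for E1 "FES therapy will be administered for one hour per session 3 times a week"; passive sessions also last one hour. A task of 30 to 45 minutes fits within a 60-minute session, so nothing forces it outside. This shows only that the schedule can be followed literally. It does not measure bias.

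4. **Is the rater kept from learning the arm?** Sections 4a, 4b, 4c, 7 and 8b do not name the SCIM rater or say where the rater sits. They mention no screen, remote rating or separate assessor. The only staff member placed at a session is the supervising physical therapist. Whether passive-arm participants wear electrodes is not stated.

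5. **What follows for the post-baseline scores?** From steps 1 to 4, Section 4c promises blinding and the schedule provides no means of keeping it for SCIM. Whether it is actually lost depends on the rater's position, which is not stated.

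6. **What follows for baseline?** Section 4a requires SCIM to fall on the MRI date and puts the first MRI before cycling. An MRI followed on the same date by the first session, with SCIM done in that session, meets both rules. There is then no strict contradiction, but the baseline SCIM is taken during the first session and not before it.

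7. **How far does it reach?** Neither Aim 1 nor Aim 2 uses SCIM, and Section 7c specifies no SCIM analysis. ISNCSCI is a separate evaluation that is not scheduled during cycling, and MRI is a separate procedure. With no SCIM standard deviation, test or model in the documents, the size of any bias cannot be calculated.

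**The case against.** The strongest reply is that absence of a description is not loss of blinding. Both arms use the same ergometer at the same target speed. Section 8b describes SCIM as a questionnaire that the participant answers, so someone who cannot see the cycle could give it. This stands: the text supports unsupported, not certainly lost. It does not rescue Section 4c, because the protocol does not provide for such a rater.

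A second reply is that rater blinding protects little when participants who know their arm answer the questions. This also stands in part. A blinded rater would remove only some of the expectation bias, but the claim in Section 4c should still be true of the outcomes it covers.

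A third is that in-session SCIM spares participants time, which C2 gives as an advantage. That is a fair reason to keep it there, provided the blinding statement is adjusted.

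A reader might also draw stronger inferences that the documents do not support:

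- **That the baseline timing is a flat contradiction.** A same-day MRI and first session satisfies both rules. Figure 1, which is not available in this copy, may settle the order.
- **That C2 gives SCIM to the FES arm only.** The protocol uses FES loosely for both arms, for instance in the passive cycling trial (B2) and in the visit payments (Section 10), and Section 4b names both E1 and E2.
- **That home FES cycling makes matters worse.** Nothing places SCIM in a home session.

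**Conclusion.** The point holds and is minor. As written, the assessor blinding in Section 4c has no support for SCIM, and it is likely lost if the rater is present at the session. That last step is an assumption, since the rater's identity and location are not stated. The baseline SCIM can be no earlier than the first cycling session, so it is not a clean pre-intervention value.

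The consequence is limited to how SCIM comparisons may be described and trusted. A reader might infer that the primary outcomes are compromised. They are not affected by this scheduling, and neither are the sample size and the planned tests. No bias size is claimed, and counting the affected scores or the share of a session that SCIM occupies would not supply one.

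**What to change.** Reconcile the study design text and C2 in Section 4a with Sections 4b and 4c.

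**Preferred.** Give SCIM outside the cycling sessions on the existing MRI and ISNCSCI dates, with baseline before the first session, by the staff whom Section 4c describes as blinded. Ask participants not to disclose their arm. Remove the in-session wording from Section 4b and C2.

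This needs no new visit date. It adds 30 to 45 minutes at each of three dates: 3 × 30 = 90 minutes to 3 × 45 = 135 minutes per participant, or 1.5 to 2.25 hours. If MRI (up to 90 minutes), ISNCSCI (up to 60) and SCIM (up to 45) share a day, the total rises from up to 150 to up to 195 minutes. Section 8b already lists time commitment as a risk, and the stated advantage of adding no time is given up. Participants may still reveal their arm.

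**If SCIM stays in session**, choose one of these and state when the baseline SCIM is taken relative to the first session:

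- Name a rater who cannot see the cycle or the stimulation and is not told the arm. The cost is arranging that separation at each assessment.
- Amend Section 4c to say that SCIM is not assessor-blinded, and interpret it accordingly. The cost is a few sentences and the loss of the blinded description for SCIM.
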